and local IRB in 2013. Our final analyses follow recommendations published in 2016 from the Second U.S. Panel on Cost-Effectiveness in Health and Medicine (Neumann et al. *Cost-effectiveness in Health and Medicine, 2nd edition*. New York: Oxford University Press. 2017). They state that cost-effectiveness analyses should include a provider and/or public payer perspective to better inform producers and payers about the intervention's costs of adoption. In updating our data sources, we incorporated methods used in the only other cost-effectiveness analysis in the peer-reviewed literature on the use of abstinence-contingent financial incentives with pregnant women who smoke (Boyd et al. Are financial incentives cost-effective to support smoking cessation during pregnancy. *Addiction*. 2016; 111(2): 360-70). More specifically, we adopted their method of translating smoking abstinence into QALY gains, which permits QALYs to be derived directly from data available in the trial based on “absolute difference percent” (ADP) (see Stapleton JA, West R. A direct method and ICER tables for the estimation of the cost-effectiveness of smoking cessation interventions in general populations: applications to a new cystine trial and other examples. *Nicotine Tob Res*. 2012; 14(4): 463-71).

The protocol information provided below is what the local Institutional Review Board approved for this randomized clinical trial comparing Best Practices, Best Practices +Financial Incentives, and Never Smokers.

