## Project Summary

Smoking during pregnancy is the leading preventable cause of poor pregnancy outcomes in the U.S. Most pregnant smokers continue smoking through pregnancy producing serious immediate and longer-term adverse health consequences for the infant. Smoking during pregnancy is highly associated with economic disadvantage and a substantive contributor to health disparities. Efficacious interventions are available, but cessation rates are low (<15%) and improvements in birth outcomes often modest or absent. Current treatments usually entail relatively brief, low-cost interventions (e.g., pregnancy-specific quitlines). There is broad consensus that more effective interventions are sorely needed. We have developed a novel behavioral economic intervention in which women earn financial incentives contingent on smoking abstinence. In a meta-analysis of treatments for smoking during pregnancy, effect sizes achieved with financial incentives were severalfold larger than those achieved with lower intensity approaches or medications. The intervention also appears to improve birth outcomes and increase breastfeeding duration. While highly promising, further research is needed in at least three areas. (1) The evidence on birth outcomes and breastfeeding is from studies that combined data across trials rather than a single prospective trial, (2) whether the intervention produces other postpartum improvements in health has not been investigated, and (3) the overall cost effectiveness of this approach has not been examined. To examine these unanswered questions, we are proposing a randomized, controlled clinical trial comparing the efficacy and cost effectiveness through one-year postpartum of current best practices for smoking cessation during pregnancy vs. best practices plus financial incentives among 230 pregnant, Medicaid recipients. We will also include a third condition of 115 pregnant nonsmokers matched to the smokers on sociodemographic and health conditions to compare the extent to which the treatments reduce the burden of smoking and to estimate how much more might be accomplished by further improvements in this incentives intervention without exceeding cost effectiveness. We hypothesize that best practices plus financial incentives will be more effective than best practices alone, that the incentives intervention will be cost effective, and that while

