### **Economic Evaluation**

**Cost analysis.** We will conduct an economic evaluation from the societal perspective including both cost-effectiveness and cost-benefit analyses (Drummond et al., 2005). The outcome measures in this trial were described above, with antepartum abstinence being primary and the related outcomes of longer-term abstinence, birth outcomes, and health and health care utilization in the 1st year postpartum important as well. Each of these outcomes can be viewed from the perspective of incremental cost effectiveness (e.g., the incremental cost to produce an additional abstinent mother at final antepartum assessment). We hypothesize that the best practices plus incentives intervention will be cost-effective (i.e., dominant) as compared to the best practices alone condition. To determine the cost of each intervention, we will employ the Brief Drug Abuse Treatment Cost Analysis Program (Brief DATCAP; French et al., 2004; French, 2010), which has been widely used in the area of

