substance abuse, including projects utilizing incentives (Knealing et al., 2008). The direct and indirect economic cost of treatment will be derived by allocating fixed costs based upon the proportion of time or space utilized by the programs (e.g., treatment facility costs), as well as costs that vary by patient engagement and smoking status (e.g., drug tests, quitline staff time, incentives). The total cost per treatment episode will be individual specific and will include the opportunity cost of the patient's time while in treatment (Salomé et al., 2003; French 2005). The time period of the cost analysis will span from intake to discontinuation or completion of the program. However, since the duration of treatment will vary according to where in the pregnancy a woman enters the study, the economic cost per person per week will also be calculated. The cost of all research-specific resources consumed will be excluded from the evaluation. All costs and benefits will be expressed in a common dollar year without the need for discounting. Estimated treatment costs will be combined with the maternal and infant health outcomes outlined above to conduct the economic evaluation. Cost-effectiveness analysis (CEA). CEA will be conducted wherein the average (mean) difference in treatment costs across the two interventions will be divided by the average (mean) difference in each outcome to derive incremental cost-effectiveness ratios (ICERs). Statistical significance of these ICERs will be determined probabilistically by employing nonparametric bootstrapped standard errors (Drummond et al. 2005). Priority will be given to comparing ratios on key birth outcome measures and NICU admissions. Additionally, a special form of CEA, cost-utility analysis (CUA), will be performed. Based upon smoking status from the quit date through one year postpartum, the number of quality-adjusted life years (QALYs) gained by the mother—as measured by the proportion of time spent in ‘smoking’ and/or ‘nonsmoking’ status—will be derived using QALY weights recommended in the extant literature (e.g., Cromwell et al., 1997; Flack et al., 2007). Women still abstinent at 1 year postpartum will be treated as long-term quitters. QALYs gained by the infant will be calculated using QALY weights recommended in the literature (Taylor et al., 2009). The incremental cost per QALY gained

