between the two modalities will be calculated and compared for mothers and infants separately and also summed across mother-infant dyads.

**Cost-benefit analysis (CBA).** CBA can often be especially useful by allowing consideration of multiple, often very different, outcomes. CBA yields two specific evaluation metrics, which are both placed in monetary terms, the benefit-cost ratio and the net benefit, that can be compared across health programs and economic sectors. We will conduct a partial CBA from a societal perspective for the intake through 12month postpartum period. Total health care costs for the mother and infant will be measured using the ‘allowed’ amounts extracted from administrative insurance claims data collected from health care providers. Adding smoking cessation treatment costs to health care costs will yield the total economic cost of care for a mother/infant dyad for the specified time period. Given randomization, the mean difference across the treatment arms (the average net benefit) will be attributed to intervention effectiveness. Cost benefit ratios also will be calculated and compared across the two treatment conditions for statistically significant differences. Sensitivity analysis. A multiway sensitivity analysis will assess the levels to which our incremental cost effectiveness ratios (ICERs) are robust to changes in component assumptions and costs. For example, while a theoretical 100% quit rate may never reach the low cost of treating the group of nonsmokers in our third condition, we can explore the maximum threshold of incentive required to maximize health benefits with respect to their costs one year postpartum. More within a realistic target, a 50% quit rate, for example, may be cost effective under all exploratory ranges of incentive compensation. The sensitivity analysis will therefore explore changes to assumptions over a broad range.

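### The ICERs are to be tested for statistical significance with no null value or willingness-to-pay reference; read as a test against zero, this asks whether costs differ, not whether incentives are good value

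*Combined protocol and SAP*

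**What the plan says.** In the Economic Evaluation section, the mean difference in treatment cost between the two randomized arms is "divided by the average (mean) difference in each outcome to derive incremental cost-effectiveness ratios (ICERs"). The inferential rule follows: "Statistical significance of these ICERs will be determined probabilistically by employing nonparametric bootstrapped standard errors". Statistical Methods sets a significance level of 0.05 throughout. Among the ICERs, birth outcomes and NICU admissions take priority.

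The economic hypothesis reads: "We hypothesize that the best practices plus incentives intervention will be cost-effective (i.e., dominant) as compared to the best practices alone condition". A cost-utility analysis follows ("The incremental cost per QALY gained" is to be compared between arms). The September 2021 entry in History of Modifications says of a published analysis, "we adopted their method of translating smoking abstinence into QALY gains". The partial cost-benefit analysis yields "the benefit-cost ratio and the net benefit", and a multiway sensitivity analysis varies the assumptions behind the ICERs. The Project Summary gives a further aim for the nonsmoker comparison: "to estimate how much more might be accomplished by further improvements in this incentives intervention without exceeding cost effectiveness".

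No null value, willingness-to-pay value, acceptability curve or confidence region for the ICERs appears anywhere, including the 2021 entry.

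**The concern.** A standard error and a significance level, with no reference value, most naturally imply a test of ICER = 0. Because the ICER is a cost difference over an effect difference, it is zero only when the cost difference is zero. The test therefore addresses whether costs differ. Whether the extra outcome is worth the extra cost depends on where the ratio lies relative to some value per unit of outcome, and the plan gives none.

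The sign does not help. Cheaper and better (dominant) and dearer and worse (dominated) both give a negative ratio.

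At stake is the basis for saying that incentives are cost-effective, one of the trial's main questions. The aim of finding how much more could be spent before value is lost cannot be answered without a reference value, and a value chosen after the results are known would be open to challenge.

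**Working it through.** The plan gives no figure for this test, so there is nothing to reproduce. The check is algebra plus a worked example.

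**Inputs from the documents:** 115 women per arm; abstinence 50% v 10%, 34% v 7% and 30% v 5%; birth weight difference 200 g with SD 550 g (all from Sample Size Justification); maximum voucher earnings $1,225 or $2,450 and projected mean payouts $613 or $1,226 (Treatment Conditions).

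**Assumed, not in the documents:** all cost distributions, QALYs per quitter (q), NICU rates and the value of a QALY (λ). In steps 2 to 5, treatment cost has mean (SD) $1,000 ($600) v $100 ($60).

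**Step 1, algebra.** Let ICER = ΔC/ΔE and z = ICER/SE. If every quitter is worth q QALYs, then ΔE = q × (abstinence difference). The ICER and its bootstrap SE are both divided by q, so z and p do not change. Multiplying all costs by k likewise multiplies both by k. This needs no cost assumption.

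**Step 2, same trial data, different q.** ΔC = 1,000 − 100 = $900; abstinence difference 0.40; 10,000 bootstrap resamples; λ = $50,000 for illustration.

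| q | ΔE | ICER | SE | z | p | NMB = λΔE − ΔC | P(NMB > 0) |
|---|---|---|---|---|---|---|---|
| 2.25 | 0.9 | $1,000 | $167 | 5.98 | 2.3e-9 | 45,000 − 900 = $44,100 | 1.00 |
| 0.0225 | 0.009 | $100,000 | $16,728 | 5.98 | 2.3e-9 | 450 − 900 = −$450 | 0.00 |
| 0.00225 | 0.0009 | $1,000,000 | $167,283 | 5.98 | 2.3e-9 | 45 − 900 = −$855 | 0.00 |

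**Step 3, mean cost shifted, SD held, q = 2.25.** Here p does change:
- ΔC $100, ICER $111: p = 0.095.
- ΔC $900, ICER $1,000: z = 5.98.
- ΔC $900,000, ICER $1,000,000: z = 6.65, p = 3.0e-11.

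**Step 4, health-care cost noise with SD $20,000, q = 2.25.** ICER $1,000: p = 0.74. ICER $10,000: p = 0.0038. ICER $1,000,000: p = 3.3e-11. The dearer QALY is the more significant one.

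**Step 5, sign.** A dominant result (ΔC = −$900, ΔE = 0.9) gives ICER −$1,000, z = −6.29, p = 3.2e-10. A dominated result (ΔC = $900, ΔE = −0.9) has the same ratio, −$1,000.

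**Step 6, how often the test would be significant.** Assumed incentive-arm cost: voucher tier (1 or 2, equal odds) × (uniform $700–1,225 if abstinent, $0–400 if not) + $300. Best-practices cost: uniform $0–100. Abstinence rows use 400 trials of 1,000 resamples; the others use 300 trials of 600.

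| Outcome and costs | Significant |
|---|---|
| Abstinence 50% v 10%, treatment cost only | 100% |
| Abstinence 34% v 7%, treatment cost only | 97% |
| Abstinence 30% v 5%, treatment cost only | 96% |
| Birth weight, 200 g, SD 550 g, treatment cost only | about 21% |
| NICU admission, assumed 5% v 12%, treatment cost only | about 9% |
| Abstinence 50% v 10%, plus health-care cost mean $15,000, SD $5,000 | about 38% |
| Same, SD $20,000 | about 5% |

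The Monte Carlo standard error is at most about 3 points (√(0.38 × 0.62/300) = 0.028).

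**The case against.** Three stronger readings are tempting, and the documents do not support them.

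- **That the plan decides cost-effectiveness by this p-value.** It does not say so. It gives no null, does not link significance to a conclusion, and its reference to a probabilistic determination could cover reading the bootstrap distribution. Zero is the natural null for a standard-error test, but it is inferred. So is applying the rule to cost per QALY, because the sentence precedes the cost-utility paragraph.
- **That p is the same whatever a QALY costs.** This holds only under proportional rescaling of costs or QALY weights; steps 3 and 4 show p moving. A constant factor fits the 2021 conversion of abstinence to QALYs. It does not fit the 2013 scheme, which uses time spent abstinent for mothers and separate infant weights.
- **That significance is nearly automatic.** The 96–100% rates apply to abstinence under assumed treatment-only costs. They fail for the prioritized birth and NICU outcomes and when health-care costs are added.

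The best defence is that the hypothesis equates cost-effective with dominant, which needs no threshold, and that effects and total cost of care are also compared separately. This has some force for dominance in the cost-benefit analysis. It does not rescue the ICER rule. The ICER numerator is treatment cost, and the incentive arm adds vouchers and abstinence monitoring to the same best-practices care, so a negative cost difference there is very unlikely. Once incentives cost more and work better, a value per unit of outcome is needed. The planned net benefit is a difference in total cost of care and puts no value on a QALY or a quitter. The sensitivity analysis supplies no benchmark, and a probability read from the bootstrap would need one too.

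**Conclusion.** The point holds in limited form. The only inferential rule stated for the ICERs has no reference value and, read as a test against zero, cannot show value for money. The invariance under proportional rescaling is exact. The example's p-values and probabilities, and the significance rates, depend on assumed costs, QALYs per quitter, NICU rates and λ.

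This is more than a missing detail, because the method named is unsuited to the question even once a null of zero is supplied. It does not show that the trial's economic conclusion would be wrong, or that it would rest on this test alone. It does not affect the abstinence or birth-outcome analyses.

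**What to change.** Replace the sentence on ICER significance with the following:

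- Resample participants within arm, keeping each woman's costs and outcomes together.
- For every outcome, report the cost difference and the effect difference separately with 95% confidence intervals, and give the ICER as a point estimate only.
- For cost per QALY, and for cost per abstinent mother, report incremental net monetary benefit (λ × effect difference − cost difference) with a 95% confidence interval, and an acceptability curve over a stated range of λ on the scale of that outcome.
- Claim dominance only from the separate cost and effect differences, never from a negative ratio.
- Use the same λ range for the question of how much more could be spent.

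For birth outcomes and NICU admissions, the separate differences and the point ICER suffice unless a value per unit is justified.

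The cost is plan wording and a small change to a bootstrap already planned, with no new data. The sponsor must choose and justify the λ range, and the conclusion becomes conditional on it. The 2021 entry describes analyses being completed, so if the range is set after results are known, the report should say so and show the whole curve.

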## **PROTECTION OF HUMAN SUBJECTS**

### **1. RISKS TO THE SUBJECTS**

#### **a. Human Subjects Involvement, Characteristics, and Design**

Participants will be 345 women seeking prenatal care at participating clinics who are insured by Medicaid. 230 women who endorse being smokers at the time that they learned of the current pregnancy will be informed that they might be eligible for a study on cigarette smoking cessation and birth outcomes while 115 women who endorse being nonsmokers will be informed that they might be eligible for a study on birth outcomes. Both will be offered the opportunity to participate in further screening to determine study eligibility.

For inclusion in the smoking cessation component, women must report being smokers at the time that they learned of the current pregnancy, report smoking in the 7 days prior to the first prenatal care visit and have that confirmed by urine toxicology testing, be 18 years of age or older, be < 25 weeks pregnant, reside in the county in which the clinic is located and immediately surrounding areas, speak English, plan on remaining in the geographical area through the pregnancy and 12-months postpartum, and provide written informed consent to participate. Failure to meet the aforementioned criteria, incarceration, untreated psychosis, current treatment with buprenorphine/methadone for opioid dependence, and refusal to participate will be reasons for exclusion.

For inclusion in the nonsmoker component of the study, women must meet the same inclusion and exclusion criteria listed above with the exception of smoking status where they must report being nonsmokers at the time they learned of the current pregnancy, report no smoking in past 6 months, not even a puff, test negative in a urine-cotinine test for current smoking, and report smoking < 100 cigarettes in their lifetime. Nonsmokers will also be matched to women in the smoker conditions on the following characteristics that may influence treatment outcome (educational attainment,

pregnancy BMI, parity, chronological age, comorbidities (i.e., diabetes, hypertension), and use of cocaine/opioids and thus could be excluded from study participation based on not aligning with our need to keep the conditions comparable on these characteristics. No participants will be excluded based on race or ethnicity. All study participants will complete informed consent. Smokers who consent to study participation will be randomly assigned to one of two treatment conditions: (1) Best practices for smoking cessation during pregnancy involving the 5 As and referral to pregnancy-specific telephone quitline counseling and self-help cessation materials or (2) Best practices for smoking cessation during pregnancy plus financial Incentives delivered contingent on smoking abstinence. Nonsmokers who consent to study participation will complete the same assessments as the smokers, but none of the smoking-cessation aspects of the study.

**b. Sources of Materials**

The research materials to be obtained include interviews, questionnaires, urine and breath specimens to verify smoking status, and medical records to assess birth and maternal and infant health outcomes through one-year postpartum.

**c. Potential Risks**

(a) A potential risk to all subjects in the proposed studies is that an unauthorized person would obtain access to the information contained in their study files. (b) There is the risk that some subjects may misuse vouchers or the money provided for completing the baseline and follow-up assessments. (c) Women in the financial-incentives condition could be enticed to use over the counter smoking cessation pharmacotherapies in order to obtain incentives, which have not been approved for use with pregnant women.

**2. ADEQUACY OF PROTECTION AGAINST RISKS**

**a. Recruitment and Informed Consent**

All participants will provide written informed consent after having a face-to-face discussion of the research with PI, Co-I or research staff designated and trained to represent the PI/Co-I in this

function. That discussion is conducted in a private setting and permits the prospective participants ample opportunity to raise questions and seek clarifications regarding the research. Later that day, the participant will take a consent form quiz to ensure she understands the critical elements of what she agreed to do (e.g. randomized to experimental or control condition, study is voluntary and can withdraw at any time). Incorrect answers will be carefully reviewed with the participant and the quiz will be readministered until all questions are answered correctly.

We operate in full compliance with HIPAA regulations. All participants in the present study will receive a HIPAA authorization form upon entry into treatment and are fully informed regarding their rights with respect to the release of personal health information. We will comply with the new regulations for protection of pregnant women in research (effective December 13, 2001). Further, as mandated by NIH, all personnel funded by this project will complete the NIH required course on Human Subjects Research Training.

### **b. Protection Against Risk**

We take the following actions to protect against the potential risks noted above: (a) All study files will be stored in locked filing cabinets. All study participants receive a participant identification code that is used in place of their name in all study data files. The key that connects participant names with identification codes is kept in a locked file and stored separately from the data files. (b) Study computers will be password protected and encrypted. (c) All voucher purchases must be approved in advance by project staff who retain veto power. If in the judgment of project staff there is a risk that the money obtained by completing the assessments might be misused, vouchers will be substituted for cash. Misuse of vouchers has not been a problem in our prior trials with this population. (d) Regarding pharmacotherapies, we inform women about the risks/benefits of over-the-counter pharmacotherapies, inform them that the use of nicotine replacement therapies will limit their ability to earn incentives, and make a recommendation that smoking cessation pharmacotherapies not be used. We have had no problems during the prior trials related to women using pharmacotherapies for smoking cessation.

